#### Exploratory Outcome Questions – Initial Patient Group

- Patient participants will be asked several questions related to exploratory outcomes:
  - Overall satisfaction with post-discharge adequacy of analgesia (Likert scale)
  - Whether patients felt they received too many, too few, or the proper amount of opioid pills
  - Whether patient required any medical visits primarily due to postoperative pain (office visits, emergency department visits, or hospital admissions)
  - Whether additional opioid refills were prescribed after the initial postoperative prescription (this will also be evaluated through EMR queries)
  - Evidence of opioid misuse (Current Opioid Misuse Measure-9 [COMM-9])

#### Assessment of Pre-Intervention Opioid Prescribing by Surgeon Participants

Baseline pre-intervention opioid prescribing by surgeon participants in both the Intervention and Control Arms will be assessed through VUMC EMR queries for all patient participants who complete the screening, consent, and pill count processes.

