## **1.5 Sample Size and Population**

**Patients (initial phase):** We anticipate successfully contacting 5 patients per day for a total of 300 patients.

**Surgeons:** We anticipate obtaining mean pre-post prescribing change in up to 60 surgeons (30 per group).

**Patients (second phase):** We anticipate successfully contacting 5 patients per day for a total of 300 patients.

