## 5 STUDY DESIGN

We plan a pilot randomized controlled trial randomizing surgeons to either intervention (direct feedback) or control (no direct feedback) arms. Surgeons frequently performing specific elective general, gynecologic, orthopedic, and neurological surgeries at VUMC will be identified during a 30-day study lead-in period. Then, patients aged at least 18 years undergoing these surgeries at VUMC during study days 1-60 will be contacted by telephone 14 days postoperatively (study days 15-74) and asked to perform an opioid pill count; they will also be asked about opioid refills, satisfaction with analgesia, emergency room visits or hospitalizations for pain, and opioid misuse. The electronic medical record will be also queried for the size of the initial postoperative opioid prescription as well as evidence of any refills for each enrolled subject. We anticipate successfully contacting 5 patients per day for a total of 300 patients in this initial phase. We plan to consent patients electronically at the time of the telephone contact as consenting patients immediately after surgery may influence their subsequent opioid consumption.

Surgeons will be consented without overt discussion of the nudge intervention. Following the first block of surgeries and associated patient follow-up (study days 1-74), data will be analyzed and then surgeons will be randomized in a 1:1 ratio to the intervention or control arms. Randomization will be stratified by both surgical specialty and by mean opioid prescription size during the initial block of surgeries. After study day 97, surgeons in the intervention arm will be provided procedure-specific direct feedback on opioid prescribing and consumption for their patients who had surgery during days 1-60.

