#### Assessment of Post-Intervention Opioid Prescribing by Surgeon Participants

Post-intervention opioid prescribing by surgeon participants in both the Intervention and Control Arms will be assessed through VUMC EMR queries for all patient participants who complete the *screening* process (primarily to exclude patients who are not opioid naïve and who may have participated earlier in the study).

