## 11 STATISTICAL CONSIDERATIONS

### 11.1 General Design Issues

This is a pilot randomized controlled trial assessing the effect of a brief behavioral nudging intervention on surgeons' postoperative opioid prescribing. In addition to determining feasibility and acceptability, we are chiefly interested in obtaining precise estimates of mean and variance to aid in planning a larger, sufficiently powered efficacy trial.

Exploratory hypotheses include that (1) surgeons in the Intervention Arm will exhibit a larger pre-post percentage change in procedure-specific prescription size (measured by oral morphine equivalents [OMEs]) compared with surgeons in the Control Arm who do not receive the nudging intervention and (2) there will be no pre-post difference between the Intervention and Control Arms in terms of patient opioid consumption, opioid refills, medical visits for pain, satisfaction with analgesia, and opioid misuse.

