#### 11.2.1 Treatment Assignment Procedures

For randomization, a list of all surgeon participants will be generated. Using random.org's sequence generator, a true random integer sequence derived from atmospheric noise will determine order in the list. Randomization will be stratified by surgical specialty (e.g., neurological surgery) and by mean opioid prescribing amount during the first 60-day surgical period prior to randomization (greater or equal to median vs. below median). We will at minimum ensure an even or near-even split among the four overall major surgical divisions (general, orthopedic, gynecologic, and neurological) across the intervention and control arms.

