### 11.4.2 Exploratory outcomes

- Mean pre-post percentage change in procedure-specific prescription size, as measured by OMEs. Mean size of post-intervention prescriptions (from electronic medical record queries) will be compared with mean pre-intervention prescription size by the same surgeon for the same procedure in order to calculate change from baseline.
- Pre-post change in patient opioid consumption, as measured by OMEs
- Pre-post change in satisfaction with overall postoperative analgesia, as measured by patient-reported numeric rating scale
- Pre-post change in patient satisfaction with general amount of opioids prescribed
- Pre-post change in incidence of medical visits for pain (office visits, emergency department visits, and/or hospital admissions)
- Pre-post change in number of subsequent opioid refills after the initial postoperative prescription (from EMR/PDMP data)
- Surgeon-reported perceived usefulness of intervention (goal: median response to question “Do you think the nudge intervention would be useful?”  $\geq 4$  on 0-5 scale, where 0 is “not at all” and 5 “extremely.”)

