## 11.5 Data Analyses

Primary feasibility and acceptability outcomes will be assessed on a descriptive basis among both the intervention and control surgeon groups (each group will be given a full explanation of the nature of the study following completion). After the intervention, we will also assess pre-post change in opioid prescription size (measured in oral morphine

equivalents) between the two groups. We will compare postoperative prescription size from the baseline (surgeries performed during days 1-60) to prescription size for surgeries performed during days 108-167. The specific exploratory outcome will be mean percentage change in procedure-specific prescription size. That is, mean size of post-intervention prescriptions (from electronic medical record queries) will be compared with mean pre-intervention prescription size by the same surgeon for the same procedure in order to calculate change from baseline. We will then compare mean per-surgeon percentage change in prescription size between the Intervention and Control Arms. We will plan a multiple regression analysis adjusting for case type and surgical specialty to further explore the targeted intervention effects.

To evaluate our other exploratory outcomes, we will assess pre-post changes across groups in patient opioid consumption, satisfaction with analgesia, medical visits for pain, opioid refills, and opioid misuse.

Additionally, we will examine differential consent rates between patients in the follow-up intervention patient group vs. those in the follow-up control patient group using descriptive statistics. This is due to the potential for varying consent rates among patients who are more or less satisfied with their postoperative analgesia following delivery of the one-time study intervention to surgeons.

We will not undersample or oversample surgeons who are women and/or members of minority racial and ethnic groups, so we expect to enroll them in proportion to their population prevalence at VUMC. We will use VUMC EMR data to assess sex/gender and race/ethnicity of patient participants, and will conduct analyses to investigate any differences between groups (including any sex/gender or race/ethnicity differences in willingness to participate in the study).

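### Baseline prescription size comes only from consented patients with a pill count, follow-up size from all screened patients, so the percentage change compares two differently defined patient sets

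*Combined protocol and SAP*

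**What the plan says.** Sections 5, 11.4.2 and 11.5 build the main exploratory outcome by setting the mean post-intervention prescription size against the "mean pre-intervention prescription size by the same surgeon for the same procedure". The resulting per-surgeon percentage changes are then averaged and compared between arms.

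The patients behind the two means are defined in section 8.2:

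- **Baseline (8.2.2).** Prescribing "will be assessed through VUMC EMR queries for all patient participants who complete the screening, consent, and pill count processes". Section 5 agrees: in the initial phase the record is "queried for the size of the initial postoperative opioid prescription as well as evidence of any refills for each enrolled subject".
- **Post-intervention (8.2.4).** Prescribing is taken "for all patient participants who complete the *screening* process". The protocol itself emphasises the word for screening, and neither consent nor a pill count is required.

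Other sections give time windows but no patient set. Section 11.5 compares "prescription size from the baseline (surgeries performed during days 1-60) to prescription size for surgeries performed during days 108-167". Section 11.2.1 stratifies surgeons "by mean opioid prescribing amount during the first 60-day surgical period prior to randomization". Section 11.1 says the team is "chiefly interested in obtaining precise estimates of mean and variance to aid in planning a larger, sufficiently powered efficacy trial".

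**The concern.** A percentage change is interpretable when numerator and denominator describe the same kind of patient. Here the denominator comes from people who were reached, agreed to take part and counted their pills. The numerator comes from everyone who passed the record screen. Part of the apparent change could therefore reflect who was counted rather than how the surgeon prescribed.

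The baseline restriction also buys nothing for this outcome. A pill count is needed for the feedback message, which sets pills consumed against pills prescribed, and for the consumption outcome. Prescription size is read from the medical record in both periods. Initial-phase candidates are screened in the record before consent (sections 8.1 and 8.2.1), and all evaluated candidates are logged (section 6.3).

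At stake are the within-arm percentage changes, the precision of each surgeon's change, and the variance carried forward to plan the larger trial.

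**Working it through.** **1. The plan's own counts.** Section 1.5: "We anticipate successfully contacting 5 patients per day for a total of 300 patients", with up to 60 surgeons, 30 per group. These reproduce: 5 × 60 days = 300 and 60/2 = 30. Patients per surgeon: 300/60 = 5, or 300/30 = 10 if only 30 surgeons take part. These are contacted patients, so they bound baseline completers from above. If 50% to 80% of contacted patients complete (assumed), 60 surgeons have 300 × 0.5/60 = 2.5 to 300 × 0.8/60 = 4 each, before any split by procedure.

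The documents give no completion rate, prescription-size spread or caseload distribution, so steps 2 to 6 are illustrative. Let c be the share of screened baseline patients who complete consent and pill count. The goal of more than 50% in section 11.4.1 has contacted patients as its denominator and does not bound c.

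**2. Within-surgeon sampling variance of the log post/pre ratio.** With n screened cases per period, the current rule gives a variance proportional to 1/(cn) + 1/n; using all screened cases gives 2/n. The ratio is (1 + 1/c)/2.

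**3. Total per-surgeon variance.** Add a between-surgeon SD of true log change, t = 0.1 to 0.3. Take a prescription-size CV of 0.3 to 0.5, with s² = ln(1 + CV²), 5 baseline completers and n = 5/c. The ratio is [t² + s²(1/5 + c/5)] / [t² + s²(2c/5)].

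| c | Within-surgeon ratio | Total ratio (range over t, CV) |
|---|---|---|
| 30% | 2.17 | 1.12 to 1.85 |
| 50% | 1.50 | 1.08 to 1.41 |
| 75% | 1.17 | 1.04 to 1.15 |
| 90% | 1.06 | 1.01 to 1.05 |

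Example: c = 50%, t = 0.2, CV = 0.5, so s² = 0.2231. The variance is 0.04 + 0.2231 × 0.3 = 0.1069 under the current rule and 0.04 + 0.2231 × 0.2 = 0.0846 with all screened cases. With 30 surgeons per arm, the SE of the arm difference is √(2 × 0.1069/30) = 0.084 against √(2 × 0.0846/30) = 0.075.

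**4. The planned percentage scale.** With no true change, the sampling SD is approximately 100 × CV × √(1/n_pre + 1/n_post). At CV = 0.5, 5 baseline and 10 follow-up cases give 50 × √0.3 = 27.4 points; 10 and 10 give 50 × √0.2 = 22.4. The squared ratio is 1.50, as in step 2.

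A small denominator also pushes the mean percentage change upward. For gamma-distributed sizes with no true change, the shift is 1/(n_pre/CV² − 1). That is 1/19 = 5.3 points with 5 baseline cases and 1/39 = 2.6 with 10; simulation gives 5.3 and 2.5.

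**5. Bias, only if completion is related to prescription size.** Let k be the completers' mean size divided by the non-completers'. With no true change, post/pre equals f = (ck + 1 − c)/k.

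| c | k = 0.9 | k = 1.1 |
|---|---|---|
| 50% | +5.6% | −4.5% |
| 75% | +2.8% | −2.3% |

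The arm difference is multiplied by f. At c = 50%, a true −20 points shows as −20 × 1.0556 = −21.1 or −20 × 0.9545 = −19.1.

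**6. Surgeons without a baseline.** With 3 screened cases and independent completion, the chance that none completes is (1 − c)³: 34.3%, 12.5%, 1.6% and 0.1% at c = 30%, 50%, 75% and 90%.

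**7. Whether the two screens match.** Section 8.2.1 fixes the opioid look-back at study days −90 to −14. Sections 6.2 and 8.2.4 count back from surgery. For a day-60 operation, 90 to 14 days before surgery is study days −30 to 46, or 77 days. The fixed window covers only −30 to −14 of these, or 17 days. For a day-1 operation it covers 76 of 77.

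**The case against.** The strongest reply has four parts.

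- **The set may be wider than section 8.2.2 implies.** Section 11.5 speaks of surgeries performed in each window and section 11.2.1 of the first 60-day period, neither mentioning consent. This stands for the stratification median, whose patient set is nowhere stated. For the outcome it does not displace the specific rule in 8.2.2, which section 5 supports. If all surgeries were intended, 8.2.2 still needs correcting.
- **The asymmetry looks deliberate and avoids the worse error.** Requiring consent after the nudge could select patients differently by arm. This stands: the screening-only rule for follow-up is sound. It argues for widening the baseline, and the documents give no reason against doing so.
- **The consequence is limited.** The outcome is exploratory, baseline selection is common to both arms, and nothing shows that completion depends on prescription size. This stands in full. Even with the assumed 10% gap, the arm difference moves by about one point in 20. A larger pilot variance would also make later planning conservative, and it would be the relevant variance if the next trial kept a consent-based baseline.
- **Most of the figures are assumed.** Only 5 (or 10) patients per surgeon comes from the plan. Holding completers at 5 when c = 30% implies 16.7 screened cases per surgeon, which no section supports. The SE example is on the log scale rather than the planned percentage scale. The no-baseline probabilities describe an edge case, since the minimum of 3 counts performed cases. These are fair limits on magnitude; they do not alter the mismatch or its direction for precision.

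**Conclusion.** The point holds, as a minor one. The plan defines the baseline and follow-up patients differently for its main exploratory outcome and leaves out baseline data that the medical record holds.

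The certain part is the mismatch and some loss of precision whenever fewer than all screened patients complete. The size of that loss depends on an unknown completion share: substantial at 30% to 50%, small at 90%. Bias in the within-arm change is possible but conditional on a link that the documents do not show. Feasibility and acceptability are unaffected, and this rule alone does not produce a spurious arm difference. The reason to act is that the pilot's stated statistical aim is a precise mean and variance, and the restriction works against it.

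**What to change.** In section 8.2.2, define baseline prescribing as the recorded prescription size for all patients of study surgeons operated on during days 1-60 who pass the same record screen as the follow-up group. The item on prior participants applies only to follow-up. Use this set for the baseline mean, the percentage change and the stratification median, and name it in sections 5, 11.2.1, 11.4.2 and 11.5.

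So that the two screens match, word the look-back in section 8.2.1 relative to the date of surgery, as sections 6.2 and 8.2.4 already do. Keep the consented pill-count subset for the consumption outcome and the feedback message. An analysis restricted to consented completers in both periods could be added as a sensitivity check.

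The cost is one sentence in 8.2.2, matching wording elsewhere and a larger record extraction for days 1-60. There is no extra patient contact. IRB permission is needed to use baseline prescription size for patients who declined or were not reached, because section 6.1 makes consent an inclusion criterion and section 13.3 limits extraction to the minimum necessary. The screening-only rule in 8.2.4 already implies a similar permission for follow-up.

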#### Randomization of Surgeon Participants

1:1 randomization of surgeon participants between Intervention and Control Arms

will be completed prior to the study intervention on approximately study day 97

### 8.2.3 Nudging Intervention (Day 97)

- On approximately study day 97, surgeon participants randomized to the Intervention Arm will receive the one-time nudging intervention.
- Procedure-specific direct feedback on patients' opioid consumption-to-prescription ratio delivered through text message, paging or email message
- Example: "Your abdominal hysterectomy patients were prescribed a mean 60 opioid pills last month. These patients consumed a mean 20 pills (33%)."

### 8.2.4 Follow-Up Patient Group Contacts and Surgeon Post-Intervention Prescribing Evaluation (Days 108-181)

#### Screening of Patient Candidates (EMR/PDMP) – Follow-Up Patient Group

- Age  $\geq 18$  years
- Undergoing specified surgeries with surgeon participants between study days 4108-167
- Provided opioid prescription that was subsequently filled
- Opioid-naïve (no prior opioid prescriptions between 14 and 90 days prior to the date of surgery)
- Non-cancer surgery
- Non-repeat/revision surgery
- Not a prior participant in the Initial Patient Group of this study
- Demographic information, including gender and race/ethnicity, will be collected
- Screening date will be recorded in the password-protected and encrypted research database

#### Assessment of Post-Intervention Opioid Prescribing by Surgeon Participants

Post-intervention opioid prescribing by surgeon participants in both the Intervention and Control Arms will be assessed through VUMC EMR queries for all patient participants who complete the *screening* process (primarily to exclude patients who are not opioid naïve and who may have participated earlier in the study).

#### Inclusion/Exclusion Criteria – Follow-Up Patient Group

- Confirmation of inclusion/exclusion criteria first assessed during preliminary screening

- Assessment of other inclusion/exclusion criteria:
  - Able to understand study procedures and participate in pill count and interview process in English or Spanish
  - Not a member of a vulnerable population (current pregnancy, prisoners)
  - Able to give informed consent (or for legal guardian/representative to do so)

#### Consent of Patient Candidates – Follow-Up Patient Group

- Identified patient candidates will be contacted by telephone or electronically by trained research coordinators.
- After description of study is provided and risks reviewed, electronic consent will be obtained.
- Documentation of electronic consent and enrollment of patient participants will be made by the research coordinator and stored in the password-protected, encrypted research database.

#### Pill Count – Follow-Up Patient Group

- Consented patients will be asked to physically obtain their prescribed opioid pill bottle and conduct a pill count.
- Patients who report having consumed the entirety of their prescription and disposed of the bottle will be considered to have a pill count of 0; absence of the empty bottle will be documented in the patient's study record.
- For patients who consent to participate but do not have their pill bottle readily available, arrangements will be made to follow up with the patient by telephone or secure electronic messaging later to complete this aspect of the query.
- All data will be stored in a password-protected and encrypted research database.

#### Exploratory Outcome Questions – Follow-Up Patient Group

- Patient participants will be asked several questions related to exploratory outcomes:
  - Overall satisfaction with postoperative analgesia (Likert scale)
  - Whether patients felt they received too many, too few, or the proper amount of opioid pills
  - Whether patient required any medical visits primarily due to

- postoperative pain (office visits, emergency department visits, or hospital admissions)
- Whether additional opioid refills were prescribed after the initial postoperative prescription (this will also be evaluated through EMR queries)
- Evidence of opioid misuse (Current Opioid Misuse Measure [COMM-9])

#### Acceptability Questions – Surgeons

- At the study’s conclusion, surgeon participants will be informed of the nature of the nudge intervention and asked several questions related to study acceptability:
  - Yes/no response to question involving perceived acceptability of receiving feedback on patients’ opioid consumption
  - Surgeon-reported perceived usefulness of intervention
- All randomized surgeons will be provided with feedback on their patients’ opioid use across the entire study at the end of the study.

## 9 SAFETY ASSESSMENTS

### 9.1 Risk/Benefit Profile and Risk Mitigation

Potential risks: We anticipate that this will be a minimal risk study. There is a small risk that people who are not connected with this study will learn a participant’s identity or their personal information through violation of HIPAA compliance and established research protocols. There is also a small risk that physicians may experience some discomfort in learning the opioid consumption patterns of their patients, or that deception was used in the initial vague description of the purpose of the study. Finally, there is a small risk that surgeon participants in the Intervention Arm may, following the intervention, prescribe insufficient amounts of postoperative opioids and consequently that patients undergoing surgery with these physicians after the intervention may be at higher risk of pain-related medical visits.

Potential benefits: There may be no direct benefits to patients participating in this study. Providers may benefit from the post-surgical opioid prescribing guidelines disseminated during the intervention. Prescribers may also be more likely to exercise more careful use of opioids after they have been made aware of discrepancies between opioids prescribed and consumed. They may also be more likely to adjust their prescribing practices, discuss opioid prescribing with colleagues, and identify careful use of opioids with their self-image in the future.

Risk mitigation: Study staff will protect the privacy of study participants. We do not

anticipate greater than minimal risk to patients or surgeons given that patient contact consists only of a pill count and several questions related to postoperative pain and the surgeon contact consists only of feedback regarding opioid prescription/consumption ratio and published prescribing guidelines. Differences in pain-related medical visits will be evaluated as described below. The consent process informs a volunteer about the study, indicates the participation is voluntary and he/she has the right to stop at any time. Risks are described during the consent process. Surgeons will be fully debriefed on the purpose of the study as soon as deception is no longer necessary (upon completion of the study).

Only designated members of the research team will have access to study data. Only data from eligible subjects will be analyzed. All data will be stored on password-protected computers and accessible only accessible to study personnel with appropriate password authorization. These measures should be effective in minimizing breaches of confidentiality. Prior to study initiation, approval will be obtained from the Institutional Review Board at Vanderbilt University Medical Center. This approval will be reevaluated each year as part of the Human Subjects Committee annual review process, paying particular attention to patient confidentiality and the Health Insurance Portability and Accountability Act of 1996 (HIPAA).

